7.4 DEMOGRAPHIC AND BASELINE CHARACTERISTICS

Demographic and baseline characteristics will include age (years) at date of informed consent, race, ethnicity, smoking status, gender, height (cm), weight (kg) at Screening, body mass index (BMI) (kg/m²) at Screening.

Demographic and baseline characteristics will be summarized by randomised treatment group and total for the Total Set. Subjects in the Total Set who were screen failures will be included in a 'Screen Fail' group for presentation purposes and included in the total column.

7.5 MEDICAL HISTORY AND CONCURRENT MEDICAL CONDITIONS

Any significant relevant illness that was resolved before screening will be recorded as medical history. Any relevant illness that is present at the day of the screening visit will be documented as concomitant illness. Medical histories and concomitant illnesses will be coded according to the Medical Dictionary for Regulatory Activities (MedDRA), current version. Medical histories and concomitant illnesses will be summarized separately, by system organ class (SOC) and preferred term (PT). Frequencies and percentages will be displayed by treatment and in total.

7.6 MEDICATION HISTORY AND CONCOMITANT MEDICATIONS

Medication history information includes any medication relevant to eligibility criteria and efficacy/safety evaluation stopped at or within 1 month prior to signing of informed consent.

Concomitant medication is any medication other than the IMP that is administered during the trial including screening. Concomitant medications will be coded using the World Health Organization Drug Dictionary (WHODrug). Concomitant medications and medication history will be summarized separately for the SAF as the frequency and percentage of patients taking each medication. If a patient took a particular coded medication more than once, the patient will be counted only once for that medication total. If a patient took more than one medication in a particular therapeutic class, the patient will be counted only once in that therapeutic class total.

A total of 10 mg of bisacodyl suppository (or an equivalent drug) may be prescribed as a standard rescue medication if a subject has no adequate BM for 3 consecutive days during the study. When bisacodyl suppository does not improve constipation, glycerin enema (or equivalent drug) may be given. Rescue treatment will be summarized for the FAS by the frequency and percentage of patients for each applied type and time to active rescue treatment.

CROSS-REGIONAL TEMPLATE

Template Number:	C-TMPL-DO-801	Page:	14 of 28
Version Number:	1.2	Effective Date:	14 Sep 2015
This version replaces:	1.1		
Parent Document:	C-SOP-DO-800		
Template Title:	Statistical Analysis Plan (Legacy Takeda)		

7.7 STUDY DRUG EXPOSURE AND COMPLIANCE

Study drug exposure and compliance will be summarized by randomised treatment group for the SAF and FAS respectively. No inferential statistics will be presented. Subject diary compliance will be presented summarized by randomised treatment group and total for the FAS for both screening and double blind periods separately.

Duration of exposure to drug (days) will be calculated as the number of days from the date of first dose to the date of last dose of study drug inclusive. So that exposure = date of last dose - date of first dose + 1. Exposure will be summarised as a continuous variable. Doses taken after Day 28 will be included in the calculation of compliance, as specified compliance is calculated up to the date of the last dose taken,

Study drug is dispensed to subjects on Day -1 only. Subjects are supplied with a bottle containing enough drug for 28 days + 2 extra days. Subjects will be required to bring their study drug bottle with them for each visit of the double blind treatment period; Day 8 (visit 3), Day 15 (visit 4) and Day 29 (visit 5). Subjects also record their daily medication intake in their diary.

Study drug compliance will be calculated by:

$$100 \times \left(\frac{\text{number of capsules taken}}{\text{number of capsules expected to be taken}} \right)$$

Overall compliance calculation is considered to indicate compliance with the dosing regimen rather than dosing duration, e.g. if a subject takes all expected doses whilst in the study but withdraws early then compliance will be considered 100%.

Overall compliance will be calculated using:

The number of capsules taken is defined as the difference between the total number of capsules dispensed and the total number of capsules remaining at the last visit.

The number of capsules expected to be taken is defined as the number of capsules prescribed per day (BID dosing) multiplied by the number of days from Day 1 to the date of last dose (last dose date - Day 1 date). If the last dose was a morning dose then this will be increased by 1, if the last dose was an evening dose then this number will be increased by 2. This is to account for the fact that the subject may stop dosing in the morning or evening of the last dose date.

CROSS-REGIONAL TEMPLATE

Template Number: C-TMPL-DO-801

Page: 15 of 28

Version Number: 1.2

Effective Date: 14 Sep 2015

This version replaces: 1.1

Parent Document: C-SOP-DO-800

Template Title: Statistical Analysis Plan (Legacy Takeda)

Week 1 compliance will be calculated as follows:

The number of capsules taken is derived from the subject diary and will be calculated as the number of completed dosing entries in the diary for the first 7 days following randomization (i.e. Day 1 to Day 7 inclusive). This should be 2 per day, a morning and evening dosing record).

The number of expected capsules to be taken will be calculated as 14 (7 days of BID dosing) if the subject has not withdrawn prior to completing 7 days of dosing. If the subject has withdrawn early (less than 7 days on treatment) then this number will be calculated as for overall compliance.

Overall study drug compliance should also be calculated from the subject's diary, where the number of tablets taken is derived from the number of completed entries (there should be 2 per day, a morning and evening record). The number of expected capsules is calculated as before. If there is a discrepancy between calculated compliance values then unless there is a recorded comment explaining the discrepancy and indicating that the diary value is correct (e.g. a comment may have been recorded indicating that some tablets were lost) the overall compliance calculated using capsule counts will be taken as the correct value.

Study drug compliance will be summarized, for overall compliance and for compliance during Week 1, as a continuous variable and additionally, as a categorical variable, with the following categories:

- Compliance < 70%
- Compliance ≥ 70% and < 90%
- Compliance ≥ 90% and < 110%
- Compliance > 110%

Compliance with the diary will also be assessed. During the double blind period there should be 2 records of study drug intake per day, note that if a dose was missed then 'Not taken' should be ticked, therefore there should be 2 entries per day, regardless of actual doses taken. Also for each day there are two questions requiring an answer (Yes/No): "Did you have bowel movement today?" and "Did you use rescue medication today?" A diary shall be considered compliant for that day if all expected entries for that day are recorded. At a minimum this will mean both questions have been answered and two drug accountability records (either time or 'Not taken'). If 'Yes' has been answered to any question then at least one related entry should be present for that day, with all expected data fields completed. Compliance during the screening period will be similar, except that no study drug intake is recorded and bowel movement is captured either as 'I did not have a bowel movement today' ticked or at least one completed bowel movement record. Subject Diaries are dispensed on Day -15 (visit 1) Day -1, Day 8 and Day 15. Diary compliance

CROSS-REGIONAL TEMPLATE

Template Number: C-TMPL-DO-801

Page: 16 of 28

Version Number: 1.2

Effective Date: 14 Sep 2015

This version replaces: 1.1

Parent Document: C-SOP-DO-800

Template Title: Statistical Analysis Plan (Legacy Takeda)

checks are conducted at each visit, except screening and follow-up. Diary compliance should be calculated as:

$$100 \times \left(\frac{\text{number of days completed}}{\text{number of days expected to be completed}} \right)$$

Subject diary compliance will be summarized, for overall compliance during the double blind period and Week 1, as a continuous variable and additionally, as a categorical variable, with the following categories:

- Compliance < 70%
- Compliance \geq 70% and < 80%
- Compliance \geq 80% and < 90%
- Compliance \geq 90% and < 100%
- Compliance = 100%

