7.7 Procedure for Reduction of Study Drug Dose Due to Adverse Events

If a subject experiences an adverse event during the Treatment Period (Double-Blind Period), the investigator may decide to reduce the dose or discontinue treatment as needed based on the type and severity of the adverse event.

For a dose reduction, either the morning (with breakfast) or evening (with dinner) dose is discontinued. As a general rule, **the investigational drug blind shall not be broken by the investigator**, even when the dose in a subject is reduced.

If the report of an adverse event from a subject calls for dose reduction at a point other than the scheduled visit, the investigator determines whether to reduce the dose in the subject. If dose reduction is determined necessary, the investigator must instruct the subject how to reduce the dose.

If the dose is reduced or treatment discontinued in a subject, the reason for dose reduction or discontinuation as well as relevant details should be recorded in the eCRF of the subject. The lubiprostone dose cannot be increased after reduction.

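### SAP 7.7 keeps expected capsules at two a day after a permitted dose reduction, so overall compliance is understated for subjects who follow the reduced regimen

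*SAP*

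**What the plan says.** **Expected and taken capsules.** In SAP 7.7, overall compliance is 100 times capsules taken over capsules expected. Taken is "the difference between the total number of capsules dispensed and the total number of capsules remaining at the last visit". Expected is "the number of capsules prescribed per day (BID dosing) multiplied by the number of days from Day 1 to the date of last dose", with a last-day correction: "If the last dose was a morning dose then this will be increased by 1", and by 2 after an evening dose. For Week 1 the expected count "will be calculated as 14 (7 days of BID dosing") unless the subject withdrew earlier. A diary-based overall figure uses the same expected count. Where the two overall figures disagree, the capsule count prevails unless a recorded comment supports the diary.

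**Aim.** The SAP states: "Overall compliance calculation is considered to indicate compliance with the dosing regimen rather than dosing duration". Its example is an early withdrawer who took every expected dose and is scored at 100%.

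**Dose reduction.** Under Protocol 7.7, after an adverse event, "the investigator may decide to reduce the dose or discontinue treatment as needed based on the type and severity of the adverse event". In a reduction, "either the morning (with breakfast) or evening (with dinner) dose is discontinued", and the dose may not go up again. Protocol 6.1 and SAP 4.2 also allow reduction in light of bowel movement frequency and consistency. Protocol Appendix A lists optional dose reduction at the Day 8 and Day 15 visits.

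**Reporting.** Drug compliance is summarized as a percentage and in four bands: below 70%, 70 to below 90%, 90 to below 110%, and above 110%. No inferential statistics are planned for it.

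**The concern.** After a reduction, the regimen the subject has been told to follow is one capsule a day. The SAP corrects the expected count for early withdrawal and for the timing of the last dose, but not for this change. It deals with dose reduction elsewhere, in the per-protocol definition (SAP 7.2) and in the sensitivity analyses of the primary endpoint (SAP 7.8.1), so the omission from 7.7 looks like an oversight.

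What is at stake is how the compliance table reads. A low percentage could mean missed doses or a reduction carried out as instructed, and the table would not separate the two. If the arms differ in how often doses are reduced, the table would show a difference in compliance that has nothing to do with missed doses.

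**Working it through.** **The plan's own figures.** Week 1: 7 × 2 = 14, as stated. Full twice-daily dosing to the evening of Day 28: expected 2 × 27 + 2 = 56, taken 56, so 100%. Withdrawal on Day 10 with every dose taken: 20/(2 × 9 + 2) = 20/20, or 19/(2 × 9 + 1) = 19/19 if the last dose was in the morning. Both give 100%, in line with the SAP's example.

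**Inputs for a reduced subject.** Treatment lasts 28 days (SAP 4.2). Let k be the number of full twice-daily days before the first reduced day. Full adherence is assumed throughout.

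- Capsules taken: 2k + (28 − k) = 28 + k.
- Expected if the evening dose is dropped (last dose is a morning dose): 2 × 27 + 1 = 55.
- Expected if the morning dose is dropped (last dose is an evening dose): 2 × 27 + 2 = 56.

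| First reduced day | k | Taken | Evening dropped | Morning dropped | Band |
|---|---|---|---|---|---|
| Day 4 | 3 | 31 | 31/55 = 56.4% | 31/56 = 55.4% | below 70% |
| Day 8 | 7 | 35 | 35/55 = 63.6% | 35/56 = 62.5% | below 70% |
| Day 15 | 14 | 42 | 42/55 = 76.4% | 42/56 = 75.0% | 70 to below 90% |

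**Where the bands change.** The score is below 70% when the first reduced day is no later than Day 11 with the evening dose dropped (38/55 = 69.1%) or Day 12 with the morning dose dropped (39/56 = 69.6%). It is below 90% up to Day 22 (49/55 = 89.1%) or Day 23 (50/56 = 89.3%) respectively. A later reduction stays in the 90 to below 110% band. Reductions starting at either visit listed in Appendix A therefore fall below 90%.

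**Week 1.** The numerator is completed diary dosing entries. If only doses taken count, a reduction from Day 2 gives 8/14 = 57.1% and one from Day 7 gives 13/14 = 92.9%. If a tick for a dose not taken also counts as completed, the score is 14/14 = 100%. SAP 7.7 expects two entries a day whether or not doses were taken, so either reading is possible. The same ambiguity applies to the diary-based overall figure.

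**Effect on an arm mean.** The documents give no reduction rate, so the rate p below is an assumption, with everyone else at 100% and the evening dose dropped. The fall in the mean is p × (100 − individual score).

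| p | Reduced from Day 8 | Reduced from Day 15 |
|---|---|---|
| 2% | 0.7 points | 0.5 points |
| 5% | 1.8 points | 1.2 points |
| 10% | 3.6 points | 2.4 points |
| 20% | 7.3 points | 4.7 points |

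**After the change.** With two capsules a day expected for k days and one a day afterwards, expected = 2k + (28 − k) = 28 + k, which equals taken. The score is 100% for every k. In Week 1, expected becomes 7 + k and the score is again 100%, provided only doses taken are counted.

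**The case against.** **The formula could mean the current prescription.** Capsules prescribed per day could be read as whatever is prescribed at the time. The parenthesis naming BID dosing, the last-day rule and the fixed 14 all point to two a day throughout, so this reading does not hold. At best, two programmers could produce different tables.

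**The stated aim concerns duration, not reduction.** The sentence on regimen is illustrated only by early withdrawal, and intake relative to the assigned twice-daily dose is a legitimate summary in itself. That is fair. It is also a reason to keep reduced intake visible, because SAP exposure is measured in days only and the compliance table is where reduced intake would otherwise show. It does not make the present percentage a measure of adherence to the regimen the subject was given.

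**The diary could correct it.** It does not correct the overall figure, because the capsule count takes precedence without a supporting comment. For Week 1 the objection stands: the error there depends on how ticks are counted.

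**Reductions are partly reported already.** Reasons for exclusion from the per-protocol set are tabulated (SAP 7.3), dose adjustment is one of them (SAP 7.2), and the adverse event record has a dose-reduced action (Protocol 10.1.11). None of these sits beside the compliance table or changes its percentages.

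**Conclusion.** The concern holds for overall compliance by capsule count. A subject who carries out a permitted reduction exactly as instructed scores about 55% to 76% when it starts between Day 4 and Day 15, instead of 100%. This assumes treatment to Day 28 and full adherence before and after the reduction. For Week 1 and the diary-based figure, the result is undetermined until the SAP says what counts as a completed entry.

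Three stronger conclusions that a reader might draw are not supported:

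- **That these subjects are classed as non-compliant.** The SAP sets no such label or cut-off for study drug. It reports a percentage and a band.
- **That the table would mainly understate adherence on lubiprostone.** No reduction rates are given for either arm. Protocol 4.1.4 reports mean daily exposure of 1.9 capsules in both arms of both earlier US studies, but does not say whether reductions were allowed there. Which arm is affected more is unknown.
- **That efficacy results are at risk.** No compliance cut-off enters the FAS or PPS, and dose-adjusted subjects leave the PPS because of the adjustment itself. The primary test is untouched.

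This is a minor correction to a descriptive table, worth making because it is cheap.

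**What to change.** In SAP 7.7, for both overall and Week 1 compliance:

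1. Define expected capsules as two a day up to the time of reduction and one a day afterwards. After a reduction, the last day adds one capsule whichever dose was kept.
2. Take the time of reduction from SAP 7.8.1 (last BID dose plus 12 hours). Protocol 7.7 requires the reason and relevant details on the eCRF but does not name a reduction date, so the SAP should give this derivation. SAP 7.8.1 covers permanent reductions for adverse events only. Section 7.7 should say that the same rule applies to reductions made under Protocol 6.1, which are documented in source notes.
3. State that the diary numerator counts only doses actually taken, not ticks for doses not taken.
4. Show the number of subjects with a dose reduction, by arm, next to the compliance table, so that reduced intake stays visible.

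The cost is a few sentences in the SAP, a small programming change and one added table row. The dosing entries needed are already in the diary. The only possible extra work is confirming that reductions made outside the adverse event route can be identified in the database.

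### Read literally, the diary rule in SAP 7.7 counts a dose ticked 'Not taken' as a capsule taken, so the descriptive Week 1 compliance summary can show 100% when doses were missed

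*SAP*

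**What the plan says.** SAP 7.7 defines study drug compliance as 100 times capsules taken divided by capsules expected. The numerator has two sources.

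- **Week 1.** Capsules taken come from the diary alone, "calculated as the number of completed dosing entries in the diary for the first 7 days following randomization". The SAP adds: "This should be 2 per day, a morning and evening dosing record". The denominator is fixed for anyone who has not withdrawn early: "The number of expected capsules to be taken will be calculated as 14 (7 days of BID dosing").
- **Overall.** The main value uses capsules dispensed minus capsules remaining at the last visit. A second value is built on what the subject wrote down: "the number of tablets taken is derived from the number of completed entries (there should be 2 per day, a morning and evening record"). If the two disagree, the capsule count is taken as correct, unless a recorded comment explains the discrepancy and supports the diary.

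The section then turns to compliance with the diary itself and describes how doses are recorded: "note that if a dose was missed then 'Not taken' should be ticked". Its conclusion on the daily total is stated in these terms: "therefore there should be 2 entries per day, regardless of actual doses taken". A complete diary day needs "two drug accountability records (either time or 'Not taken'"). Protocol 8.2 likewise tells subjects to note a missed dose in the diary.

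**The concern.** The same count serves two purposes. In the compliance calculation, two completed entries a day mean two capsules taken. In the description of the diary, two completed entries a day are expected whether or not any capsule was taken. If a 'Not taken' tick is a completed entry, a subject who follows the instructions and records a missed dose has that dose counted as taken. The result is then a measure of how fully the dosing record was filled in, which 7.7 already covers with a separate diary-compliance formula.

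Week 1 matters most because it is the primary-endpoint week and the SAP gives it its own compliance table. That table has no capsule-count override. Duration of exposure, which runs from first to last dose, cannot show skipped doses either. At stake is whether the report describes Week 1 adherence correctly.

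**Working it through.** **Inputs, all from SAP 7.7.** Week 1 denominator 14. Numerator: completed diary dosing entries. A missed dose is recorded as a 'Not taken' tick. Categories: below 70%; 70% to below 90%; 90% to below 110%; above 110%.

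**Reproducing the plan's figure.** 7 days × 2 capsules a day = 14, as stated.

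**Week 1 formulas.** Let m be the number of missed doses, each ticked 'Not taken', in a subject who stays on study for the 7 days with a complete diary.

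- Literal rule: 100 × 14/14 = 100% for every m.
- Timed entries only: 100 × (14 − m)/14.

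| Missed and ticked (m) | Literal rule | Timed entries only | Correct category |
|---|---|---|---|
| 0 | 100% | 100% | 90% to <110% |
| 1 | 100% | 13/14 = 92.9% | 90% to <110% |
| 2 | 100% | 12/14 = 85.7% | 70% to <90% |
| 4 | 100% | 10/14 = 71.4% | 70% to <90% |
| 5 | 100% | 9/14 = 64.3% | <70% |
| 7 | 100% | 7/14 = 50.0% | <70% |

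The literal rule puts every row in the 90% to below 110% category. The category is right for m = 0 or 1 and wrong from m = 2 upward.

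**Ticked against blank.** A missed dose left blank is not a completed entry, so it is not counted. Two subjects who each miss five doses would score 100% if the misses were ticked and 9/14 = 64.3% if they were left blank. The better record-keeper gets the wrong value.

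**Overall diary value.** For a last dose on the evening of Day 28, the SAP's expected count is 2 × 27 + 2 = 56. With 6 ticked misses, the timed-entry value is 50/56 = 89.3%; with 17 it is 39/56 = 69.6%. The literal value is 100% in both cases. These literal values reach the report only where a comment makes the diary prevail. Otherwise the capsule count replaces them.

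**The case against.** The strongest defence is that this is a matter of wording. The quantity being defined is capsules taken, and a dosing entry can naturally be read as the record of a dose. The 'Not taken' text belongs to the paragraph on diary compliance, which is a separate measure. Comparing the diary value with the capsule count makes sense only if the diary value counts capsules, and two entries a day also describes full adherence. A programmer could well count only timed entries. That reading is possible, but 7.7 does not state it, and its two-per-day expectation is the same count that the section later says holds whatever was taken. A definition that allows 100% and 64.3% for one subject needs settling.

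Several limits on the consequences stand:

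- **Size.** No document gives a missed-dose rate near 5 of 14; that row is illustrative. Protocol 4.1.4 reports a mean of 1.9 capsules a day in both arms of the two US trials. That is 1.9/2 = 95%, or about 0.7 missed doses a week (14 × 0.05). A single ticked miss does not change the category. Individual subjects may miss more than the mean.
- **Adverse events.** A reader might infer that under-dosing because of adverse events would go unseen. The documents do not support that in general. Dose reductions and their reasons are recorded on the eCRF, and subjects with an adjusted dose leave the per-protocol set. SAP 7.8.1 plans a sensitivity analysis for permanent AE-related reductions, with an exception if fewer than 5% of subjects reduce in the first week. What remains is skipped doses with no recorded reduction.
- **Day 8 check.** A reader might also infer that no other Week 1 adherence information exists. Protocol 9.3.3 and Appendix A provide for drug accountability at the Day 8 visit. The SAP does not use that count for the Week 1 value.

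**Conclusion.** The point holds as a defect of definition in a descriptive summary. Under the literal rule, Week 1 compliance is 100% for any fully completed diary, and subjects with two or more ticked misses are placed in too high a category. This assumes that 'Not taken' ticks count as completed entries, that subjects tick them as instructed, and that they remain on study through Day 7. The number of subjects affected cannot be estimated, because the documents give no distribution of missed doses for this trial.

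It would be tempting to conclude that the primary result or the per-protocol analysis is compromised. The documents do not support that. SAP 7.7 plans no inferential statistics for compliance, the primary test uses the FAS as randomized, and no compliance threshold is among the listed per-protocol exclusions. Nor is reported overall compliance generally wrong, because the capsule count prevails unless a recorded comment supports the diary.

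**What to change.** In the Week 1 paragraph of SAP 7.7, define capsules taken from the diary as the number of dosing entries with a recorded intake time, and state that 'Not taken' entries are excluded. Use the same definition for the overall diary calculation. Leave the diary-compliance measure unchanged; there a 'Not taken' tick rightly counts as a completed record.

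The cost is one phrase in the SAP and one condition in the program. The diary already separates an intake time from a 'Not taken' tick, so no new data are needed.
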